### **8.3.4 Removal of Subjects from Therapy or Assessments**

Every attempt must be made to gather complete follow-up data for all subjects enrolled. Subjects who would be traveling, relocating or otherwise unavailable for the postoperative follow-up schedule should not be chosen for the study.

Subjects should be discontinued from the study only if irretrievably lost to follow-up for unavoidable reasons such as inability to locate, subject uncooperativeness, subject illness, or subject death. A subject may also be discontinued from the study if complications occur during surgery and the subject does not receive XEN or undergo trabeculectomy. If a subject does receive XEN or undergo trabeculectomy following complications, then the subject should be followed up per the study protocol. Also, if the eye undergoes additional glaucoma surgery after the study intervention due to poor IOP control, it will be discontinued from the study as a failure.

In the event that a subject is discontinued from the study, the investigator shall complete a Subject Exit Form in the electronic data capture (EDC) system, indicating the early termination reason.

Subjects may withdraw their consent to continue in the study at any time. Subjects withdrawing from the study after receiving XEN or undergoing trabeculectomy will be encouraged to complete the same final evaluations as subjects completing the study according to this protocol, particularly safety evaluations. The aim is to record data in the same way as for subjects who completed the study. Subjects who discontinue before undergoing a study surgery will not be required to return for study follow-up visits.

Reasonable efforts will be made to contact subjects who are lost to follow-up. These efforts must be documented in the subject's file.

The sponsor has the right to terminate the study at any time, in case of SAEs, or if special circumstances concerning the study product or the company itself occur, making further treatment of subjects impossible. In this event, the investigator(s) will be informed of the reason for study termination.

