### **11.1.1 Datasets or Populations Analyzed**

The Enrolled population consists of all study eyes for which the subject has signed the ICF. The Enrolled population will be used to summarize disposition data.

The Intent-to-treat (ITT) population consists of all enrolled eyes randomized to study glaucoma surgery (XEN or trabeculectomy). The ITT population will be the primary analysis population for effectiveness data. Subject demographics, baseline characteristics, and PRO data will be analyzed using the ITT population. Subjects will be grouped and analyzed according to the actual surgery received.

The Modified Intent-to-treat (mITT) population consists of eyes in the ITT population that receive study glaucoma surgery and have no major protocol deviations, which will be defined in the SAP and identified prior to database lock. The mITT population will be used for selected effectiveness endpoints (as specified in the SAP), and will be used for the analyses of PRO data also.

The Safety population consists of all enrolled eyes that undergo study glaucoma surgery, whether surgery is completed or aborted, and have follow-up visits or evaluations. The Safety population will be used to analyze AEs, medical and ophthalmic history, and concomitant medications (ocular and systemic). Subjects will be grouped and analyzed according to the surgery they received.

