SAS PROC POWER with the case of TWOSAMPLEFREQ is employed to yield a total sample size of 102 completors (68 in XEN and 34 in Trab). As a result, the study requires to enroll a minimum of 114 patients (76 in XEN and 38 in Trab) in order to achieve the study goal when 10% dropout rate is taken into account.

CONFIDENTIAL

Draft Statistical Analysis Plan v2.0

XEN-45 Gel Stent

4. Populations for Analysis

The analysis populations will consist of participants as defined below:

- **Enrolled population:** For all study eyes for which subjects have signed ICF and met all inclusion/exclusion criteria.
- **Intent-to-Treat (ITT) population:** all enrolled eyes randomized to study glaucoma surgery (XEN or trabeculectomy), and received study glaucoma surgery (XEN or trabeculectomy).
Note that analyses will be based on the randomized surgery.
- **Safety Population :** All enrolled eyes that have undergone study glaucoma surgery.
Note that analyses will be based on the actual surgery treated.

Due to the nature of Phase 4 study, there will be no mITT population to be implemented, unless there are significant protocol deviations or other reasons.

CONFIDENTIAL

Draft Statistical Analysis Plan v2.0

XEN-45 Gel Stent

5. Statistical Analyses

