6.3.3. Protocol Deviations

Participants reporting major protocol deviations will be summarized in total and by treatment group for the ITT population.

The major protocol deviations that are thought to potentially affect the analysis will be reviewed and finalized in a blinded manner prior to the data base lock. The major deviations are following:

- Prior XEN/trab/tube in study eye
- Prior transscleral ablative procedures in study eye
- No baseline IOP /IOP-lowering medication count recorded
- Wrong study procedure performed
- XEN not implanted (surgery aborted)

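### No rule scores an eye whose assigned procedure is started but not delivered, and the protocol and SAP disagree on its population and arm

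*Protocol*

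**What the plan says.** **Protocol 8.3.4.** For intraoperative complications: "A subject may also be discontinued from the study if complications occur during surgery and the subject does not receive XEN or undergo trabeculectomy". The next sentence covers the remaining eyes: "If a subject does receive XEN or undergo trabeculectomy following complications, then the subject should be followed up per the study protocol". For additional glaucoma surgery after the study intervention because of poor IOP control, the status is explicit: "it will be discontinued from the study as a failure". An undelivered procedure gets no such label.

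**Protocol 11.1.1.** "The Intent-to-treat (ITT) population consists of all enrolled eyes randomized to study glaucoma surgery (XEN or trabeculectomy"; that is, all randomised eyes. The same paragraph adds: "Subjects will be grouped and analyzed according to the actual surgery received". The Safety population is "all enrolled eyes that undergo study glaucoma surgery, whether surgery is completed or aborted, and have follow-up visits or evaluations", also grouped by surgery received.

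**SAP section 4.** ITT is narrowed to randomised eyes that also received study surgery, and is analysed by randomised surgery. Safety is the enrolled eyes that have undergone study surgery, with no mention of aborted operations. For Safety: "Note that analyses will be based on the actual surgery treated".

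**SAP 6.3.3.** Major deviations, to be summarised by treatment group in ITT, include "XEN not implanted (surgery aborted" and performance of the wrong study procedure.

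**SAP 5.3.1 and 5.3.2.** A responder must meet five criteria: the IOP reduction, no increase in topical medications, no clinical hypotony, no loss of vision to count fingers, and no secondary glaucoma surgical intervention. Missing data are not imputed.

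**The concern.** The point concerns eyes taken to theatre whose assigned operation is begun and not completed as assigned. Eyes that never reach surgery are a different matter. Being unable to deliver a procedure is a result of choosing that procedure, so it belongs in a comparison of two surgical strategies. If such eyes disappear from the denominator more often in one arm, that arm's success rate is flattered. In a one-sided non-inferiority test of XEN, loss on the XEN side favours the claim.

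The safety side matters too. An operation abandoned because of a complication is one whose events a safety table should hold. Under the SAP it is unclear whether that eye is in the population at all. For an eye that had a XEN attempt and then a trabeculectomy, it is unclear which column receives the events of the attempt.

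**Working it through.** **1. Following one eye through the rules**

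| | Aborted, nothing delivered | Randomised to XEN, converted to trabeculectomy in the same session |
|---|---|---|
| Protocol 8.3.4 | May be discontinued; no outcome status | Appears to stay in follow-up |
| Protocol ITT | In (randomised), but grouped by a surgery not received | In, under trabeculectomy |
| SAP ITT | Out, if an abandoned attempt is not surgery received; in, according to SAP 6.3.3 | In, under XEN |
| Protocol Safety | In, if there is any follow-up or evaluation | In; trabeculectomy on the natural reading |
| SAP Safety | Undefined: aborted surgery not mentioned | In; trabeculectomy on the natural reading |
| Primary endpoint | No criterion applies; missing if there is no Month 12 visit | Scored on the five criteria; unclear whether conversion is a secondary glaucoma surgical intervention |

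The aborted eye also falls between the follow-up rules. Protocol 8.3.4 encourages final evaluations after XEN or trabeculectomy has been received, and excuses subjects who discontinue before surgery. An abandoned operation is neither.

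**2. The plan's own figures**

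Inputs: trabeculectomy success 0.70, margin 24 points, 68 + 34 = 102 completers, 10% dropout (all SAP section 3). XEN success is taken as 0.70, and 80% power is carried over from the protocol calculation; both are assumptions.

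Trabeculectomy n = (z₁₋α + z₀.₈₀)² × (0.21/2 + 0.21) / 0.24². At one-sided 5% this is 2.486² × 0.315 / 0.0576 = 33.8, so 34, with 68 XEN: 102, as stated. 102/0.9 = 113.3, so 114 enrolled (76 + 38), as stated.

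**3. Effect on the XEN rate**

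The abort number a is assumed, because the documents give none. Take 70% success among 68 XEN completers, 0.70 × 68 = 47.6, with a aborted eyes in addition.

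| a | Share of 76 | Left out | Counted as failures, 47.6/(68 + a) | Gap |
|---|---|---|---|---|
| 2 | 2.6% | 70.0% | 47.6/70 = 68.0% | 2.0 points |
| 4 | 5.3% | 70.0% | 47.6/72 = 66.1% | 3.9 points |
| 8 | 10.5% | 70.0% | 47.6/76 = 62.6% | 7.4 points |

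Eight aborts would use the whole XEN dropout allowance (76 − 68 = 8), so the last row is an extreme.

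**4. Effect on the difference between arms**

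The margin applies to the difference, so trabeculectomy aborts matter. Success among 34 completers is 0.70 × 34 = 23.8. With 4 XEN aborts counted as failures:

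- No trabeculectomy aborts: 66.1% − 70.0% = −3.9 points.
- One: 23.8/35 = 68.0%; difference −1.9 points.
- Two (the same rate under 2:1 allocation): 23.8/36 = 66.1%; difference 0.

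**5. Can it change the decision?**

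Use the SAP section 2 rule (lower 95% limit above −24%) with 24/34 trabeculectomy responders. With 4 XEN aborts left out, 43 responders of 64 suffice. With the 4 counted as failures, 45 of 68 are needed. A trial with 43 or 44 XEN responders would pass under one handling and fail under the other.

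**6. Effect on power**

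Power = Φ[(0.24 + p_X − 0.70)/SE − 1.96], with SE² = p_X(1 − p_X)/n_X + 0.21/34. Here k of the 68 XEN eyes fail in theatre and none do in the other arm; counted as failures, p_X = 0.70 × (68 − k)/68. With k = 0, SE = 0.0963 and power is 70.3%. It is below 80% because 102 corresponds to one-sided 5% while the decision uses a 95% interval, which is a separate matter.

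| k | Power, left out | Power, counted as failures |
|---|---|---|
| 1 | 70.1% | 66.2% |
| 2 | 69.9% | 62.0% |
| 4 | 69.4% | 53.3% |
| 7 | 68.7% | 40.2% |

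**The case against.** A reader might infer that a XEN attempt that fails in theatre can never count against XEN. The documents do not support that. Under the SAP's as-randomised ITT a converted eye stays in XEN and is a non-responder if it misses any criterion, and a same-session trabeculectomy might itself be read as a secondary glaucoma surgical intervention. An aborted eye that stays on study and later has glaucoma surgery can also fail. SAP 6.3.3 places aborted XEN eyes in ITT. The SAP version history says its ITT definition was changed because of patients terminated before treatment, which suggests that abandoned operations were not the target.

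Protocol 8.3.4 is permissive, covers both arms and opens by asking for complete follow-up. It never describes conversion; its second sentence can simply mean that the assigned operation was completed after a complication.

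A reader might also infer that the safety comparison is reversed. That goes too far. SAP Safety omits aborted surgery but does not exclude it, and by dropping the protocol's follow-up condition it is broader in one respect. A device malfunction before implantation is a listed event of interest, adverse device effects are tabulated separately, and listings of all AEs are planned. The arm for an eye exposed to both procedures is unstated.

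Finally, the abort rate is invented, and equal rates remove the shift in the difference.

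All of this stands against the stronger readings. It does not supply the missing rule: no text says how an aborted or converted eye scores, and the two documents conflict on membership and arm.

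**Conclusion.** The concern holds as a gap and a contradiction. Non-delivery of the assigned procedure has no scoring rule. SAP section 4 and SAP 6.3.3 point different ways on whether an aborted eye is in ITT, and the protocol and SAP group ITT on opposite principles. SAP Appendix 2 records only the sample size reduction as a change, not the changed membership or grouping.

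The direction of any bias is conditional. It favours XEN only if aborts are more frequent in that arm and those eyes are left out. The illustrated gap of 2.0 to 7.4 points in the XEN rate assumes 2 to 8 aborts and 70% success otherwise. The net effect on the difference runs from that size down to zero as trabeculectomy aborts approach the same rate. The real size is unknown. The contradictions do not depend on it, and a few eyes could decide a result near the margin. This should be fixed, but it does not show that the primary result is biased.

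**What to change.** 1. **SAP 4 and 5.3.1:** keep every randomised eye taken to surgery in ITT in its randomised arm. Count an aborted, undelivered procedure as a non-response, in either arm.
2. **SAP 5.3.1:** state whether a same-session conversion is a secondary glaucoma surgical intervention, and run a sensitivity analysis the other way. Either choice can be defended as an estimand, but it has to be made before the data are seen.
3. **SAP 4, Safety:** restore the protocol's inclusion of both completed and aborted surgery, and tabulate intraoperative events by the procedure being attempted when they occurred.
4. **Protocol 11.1.1 and 8.3.4:** delete the sentence that groups ITT by actual surgery, so that both documents use the randomised arm. Reconcile the discontinuation sentence in 8.3.4 with that section's own requirement to gather complete follow-up data.
5. **SAP Appendix 2:** record the changes to ITT membership and grouping.

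The cost is SAP wording, a short protocol amendment and possibly a few extra follow-up visits. The reported XEN success rate may be slightly lower, and power falls as in step 6 if aborts occur mainly with XEN.

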## **8.4 Investigated in Protocol**

### **8.4.1 Study Product and Procedures**

#### **8.4.1.1 XEN**

XEN is manufactured by Allergan, Plc (Ireland). XEN is composed of a gelatin derived from porcine dermis, formed into a tube, and cross-linked with glutaraldehyde. It is intended to be inserted in the angle and through the sclera, connecting the anterior chamber to the subconjunctival space. XEN is preloaded in the XEN Injector, a single-use mechanical delivery system. XEN is packaged with directions for use and the procedure to insert XEN should be carried out in line with surgical training provided by the manufacturer and following the standard of care at each investigative center.

#### **8.4.1.2 Comparator – Trabeculectomy**

Trabeculectomy will be performed in accordance with the standard of care at each investigative center with adjunctive antifibrotic therapy and including essential steps: conjunctival flap, scleral flap, and sclerostomy. Note: Peripheral iridectomy is not mandated and is left to the standard practice of the surgeon.

### **8.4.2 Packaging and Labeling**

XEN used will be commercial supply of XEN-45 Gel Stent in the United States.

### **8.4.3 Device Complaint Reporting**

Device complaints and malfunctions should be reported per the package insert or directions for use.

### **8.4.4 Method of Assigning Subjects to Treatment Groups**

Subjects will be randomized by investigational site to a 2:1 (XEN:trabeculectomy) randomization schedule by the Medidata Rave RTSM (Randomization and Trial Supply Management) application. The randomization list will be generated by the sponsor's independent Randomization Services Group using a customized validated system composed of a series of SAS® Macros (version 1.4). This list will be provided to the contract research organization's (CRO's) independent randomization team, who will upload the list into the Medidata Rave RTSM application and validate it. Upon completion of a randomization electronic case report form (eCRF), indicating that a study eye meets all entry criteria, the data will be sent to the RTSM system for randomization. The RTSM system will then provide the surgery group assignment for the study eye and integrate it back into the randomization eCRF. The sponsor's and CRO's study team members, investigational site staff, and subjects will not have access to the randomization list.

#### **8.4.5 Prior and Concomitant Therapy**

Topical IOP-lowering medication may be stopped 1 to 4 weeks before surgery and re-started according to the investigator's recommendation. At baseline, subjects are to be using at least 1 topical IOP-lowering medication and, when using that medication at the maximum tolerated dose, their IOP is not controlled. After the subject is determined to be eligible for participation in the study and is enrolled, the physician may stop the previously prescribed medications 1 to 4 weeks before surgery and begin preoperative medications (eg, steroids, antibiotics, artificial tears) to prepare the ocular surface before surgery. The detection and treatment of comorbid conditions, particularly diseases of the ocular surface disease (dry eye) and blepharitis, can help reduce eye inflammation (Baudouin 2012). Stopping or reducing IOP-lowering medications and replacing them, if necessary, with oral acetazolamide prior to surgery may be considered along with use of topical steroids and preservative-free lubricants to reduce ocular surface inflammation and improve the likelihood of successful implantation (Vera et al. 2018).

Subjects who have had prior ab-externo incisional glaucoma surgery (such as trabeculectomy, viscocanalostomy, canaloplasty, tube shunts of any type, collagen implants, etc), conjunctival filtering surgery (such as XEN), transscleral cycloablative procedures (such as cyclophotocoagulation, micropulse cyclophotocoagulation, cryotherapy, UC3, etc) or prior major conjunctival surgery (ie, scleral buckle) are not eligible for the study (see Section 8.3.3).

Perioperative adjunctive antifibrotic therapy should be used according to physician training and practice.

## **9 TIMING OF STUDY PROCEDURES**

The planned study assessments are in [Section 8.1.2](#).

Every attempt should be made to schedule the visits (specifically measurement of IOP) at approximately the same time of day to avoid the influence of diurnal fluctuations. Assess IOP using Goldmann applanation tonometry. Take 2 measurements. If the first 2 measurements differ by more than 3 mm Hg, take a third measurement. Use the average if 2 measurements are taken (or the median if 3 measurements are taken) to determine each day's IOP.

### **9.1 Pretreatment Visits**

#### **9.1.1 Baseline Qualifying Visit**

During the study Baseline Qualifying Visit, the procedures will be performed following the Schedule of Assessments ([Table 8.1](#)).

When these procedures have been performed, the next visit will be scheduled. The Baseline Qualifying Visit and Preoperative Visit may occur on the same day if there are no changes to the IOP-lowering medications prior to surgery.

#### **9.1.2 Preoperative Visit (Visit 1)**

During the study Preoperative Visit, the procedures will be performed as shown on the Schedule of Assessments ([Table 8.1](#)).

This visit may be repeated as necessary to complete required examinations. The visit window for Preoperative Visit 1 (including any repeated visits) is up to 4 weeks before study glaucoma surgery in the study eye and  $\geq 3$  months since previous intraocular surgery in either eye. When all Visit 1 procedures have been performed, if all entry criteria are met, the study eye will be randomized to glaucoma surgery procedure, and the next visit will be scheduled.

#### **9.1.3 Operative Visit (Visit 2)**

The Operative Visit (Visit 2) will be Day 0 of the study. At this visit, glaucoma surgery (XEN or trabeculectomy) will be performed. Record any intraoperative complications.

### **9.2 Postoperative Visits**

#### **9.2.1 Day 1 (Visit 3)**

The first postoperative visit will take place on study Day 1 (6-48 hours) after the Operative Visit. During this visit the procedures will be performed following the Schedule of Assessments ([Table 8.1](#)).

#### **9.2.2 Week 1 (Visit 4)**

Visit 4 will take place 1 week (3-10 days) after the Operative Visit. During this visit the procedures will be performed following the Schedule of Assessments (Table 8.1).

#### **9.2.3 Week 2 (Visit 5)**

Visit 5 will take place 2 weeks (11-20 days) after the Operative Visit. During this visit the procedures will be performed following the Schedule of Assessments (Table 8.1).

#### **9.2.4 Month 1 (Visit 6)**

Visit 6 will take place 1 month (3-8 weeks) after the Operative Visit. During this visit the procedures will be performed following the Schedule of Assessments (Table 8.1).

#### **9.2.5 Month 3 (Visit 7)**

Visit 7 will take place 3 months (9-17 weeks) after the Operative Visit. During this visit the procedures will be performed following the Schedule of Assessments (Table 8.1).

#### **9.2.6 Month 6 (Visit 8)**

Visit 8 will take place 6 months (18-32 weeks) after the Operative Visit. During this visit the procedures will be performed following the Schedule of Assessments (Table 8.1).

#### **9.2.7 Month 9 (Visit 9)**

Visit 9 will take place 9 months (33-47 weeks) after the Operative Visit. During this visit the procedures will be performed following the Schedule of Assessments (Table 8.1).

#### **9.2.8 Month 12 (Visit 10)**

Visit 10 will take place 12 months (48-60 weeks) after the Operative Visit. During this visit the procedures will be performed following the Schedule of Assessments (Table 8.1).

#### **9.2.9 Early Withdrawal Visit**

In the case of an early withdrawal, an Early Withdrawal Visit should be scheduled for subjects who underwent a study surgery, if possible. Procedures should be performed as for the Month 12, Visit 10.

### **9.3 Duration of Study**

The duration of study participation will be approximately 12 months.

---

#### **9.4 Pregnancy**

If a female XEN subject becomes pregnant during the study, the investigator will notify Allergan immediately by completing the Pregnancy Surveillance Form after the pregnancy is confirmed and faxing it to [contact] or [contact]. Best practices are to be followed to ensure the welfare of the subject and the fetus. Once the pregnancy has reached term, the second page of the Pregnancy Surveillance Form concerning outcome is to be completed. The medical safety physician will contact the investigator to obtain information about the pregnancy outcome. The subject will continue to be followed up as part of the implanted population. Pregnancy by itself will not be considered an AE or SAE. Hospitalization for a normal delivery or elective abortion of a normal fetus does not constitute an SAE. However, the occurrence of an adverse pregnancy outcome for the mother or child may constitute an AE or SAE, and these are to be reported.

